8. PRESTUDY AND CONCOMITANT THERAPY

Prestudy therapies (prescriptions or over-the-counter medications, including vitamins and herbal supplements, nonpharmacologic therapies such as electrical stimulation, acupuncture, special diets, or exercise regimens) administered within 30 days before the start of screening must be recorded at screening. Consumption of large quantities of grapefruit juice (>1 liter/day) and phlebotomy is disallowed from baseline until EOT and from screening until the Week 12 Follow-up Visit, respectively.

All therapies (prescription or over-the-counter medications, including vaccines, vitamins, herbal supplements; nonpharmacologic therapies such as electrical stimulation, acupuncture, special diets, or exercise regimens) used during the study and different from the study drugs (AL-335, ODV, and SMV) must be recorded in the eCRF. Recorded information will include a description of the type of drug, Treatment Period, dosing regimen, route of administration, and its indication. Patients on disallowed medication (see Table 1) are excluded from the study. Modification of an effective preexisting therapy should not be made for the explicit purpose of entering a subject into the study.

For study-specific rules on the use of contraceptive methods, refer to Section 4.1.

AL-335 is metabolized by esterases and is not a substrate of any CYP enzymes. AL-335 (and metabolites) has demonstrated a very low inhibition potential to CYP1A2, CYP2B6, CYP2C8, CYP2C9, CYP2C19, CYP2D6, and CYP3A. AL-335 is a substrate for P-gp but does not inhibit P-gp. Coadministration of AL-335 with inhibitors of P-gp may increase AL-335 plasma concentrations. ALS-022399 and ALS-022227 are neither substrates nor inhibitors of P-gp, OATP1B1, OATP1B3, OAT1, OAT3, or OCT2 transport.

ODV has demonstrated a low inhibition potential for CYP1A2, CYP2B6, CYP2C8, CYP2C9, CYP2C19, CYP2D6, and CYP3A. ODV is primarily cleared by biliary secretion, is not significantly metabolized, and is not expected to be involved with clinically significant DDIs associated with the CYP enzyme system. ODV is neither a substrate nor an inhibitor of transporters such as OATP1B1, OATP1B3, breast cancer resistance protein, MRP2, MRP3, and bile salt export pump. ODV is a low-affinity substrate of OATP1B1 and does not inhibit OATP1B1. ODV is not a substrate but is an inhibitor of P-gp. Coadministration of ODV with drugs that are substrates for P-gp transport may result in increased plasma concentrations of such drugs.

SMV is a mild inhibitor of intestinal CYP3A. Coadministration of SMV with drugs that are primarily metabolized by CYP3A may result in mild increases in plasma concentrations of such drugs, which could increase or prolong therapeutic effect and adverse reactions of CYP3A substrates with narrow therapeutic index. Drugs that induce CYP3A may decrease SMV plasma concentrations and reduce the therapeutic effect of SMV. Coadministration of SMV with inhibitors of CYP3A may increase SMV plasma concentrations. Clinically, SMV inhibits uptake transporters OATP1B1, OATP1B3, and the efflux transporters P-gp/MRP1 and MRP2. Coadministration of SMV with drugs that are substrates for OATP1B1, OATP1B3, and P-gp transport may result in increased plasma concentrations of such drugs.

An overview of disallowed concomitant medications is presented in Table 1.

Table 1: Disallowed Medications
Disallowed within 30 days of screening until the end of follow up
• All nonHCV investigational drugs or invasive investigational medical devices
• Experimental nonHCV vaccines
Note: Approved nonHCV vaccines are allowed.
Disallowed within 3 months prior to screening until the end of the study
• Antiarrhythmic: amiodarone
Disallowed from screening until the end of the study
• All concomitant medications with a potential to prolong QT interval (eg, digoxin)

NCT02993250

Clinical Protocol 64294178HPC2003 Amendment 5

- Drugs associated with QT prolongation and/or Torsades de Pointes (QT Drug Lists by Risk Groups) provided by the Arizona Center for Education and Research on Therapeutics:
 - Amantadine, Amitriptyline, Amphotericin B, Anagrelide, Apomorphine, Aripiprazole, Arsenic trioxide, Asenapine, Atazanavir, Atomoxetine, Azithromycin, Bepridil, Bortezomib, Bosutinib, Buprenorphine, Capecitabine, Ceritinib, Chloral hydrate, Chloroquine, Chlorpromazine, Cilostazol, Ciprofloxacin, Citalopram, Clarithromycin, Clomipramine, Clozapine, Cocaine, Crizotinib, Dabrafenib, Dasatinib, Degarelix, Delamanid, Dexmedetomidine, Diphenhydramine, Disopyramide, Domperidone, Donepezil, Droperidol, Efavirenz, Eribulin mesylate, Erythromycin, Escitalopram, Esomeprazole, Famotidine, Fingolimod, Flecainide, Fluconazole, Fluvoxamine, Foscarnet, Furosemide, Galantamine, Garenoxacin, Gatifloxacin, Granisetron, Haloperidol, Hydrochlorothiazide, Hydroxychloroquine, Hydroxyzine, Imipramine, Indapamide, Itraconazole, Ketoconazole, Lansoprazole, Lapatinib, Leuprolide, Levofloxacin, Levomepromazine, Lithium, Loperamide, Methadone, Metoclopramide, Metronidazole, Mirabegron, Mirtazapine, Moxifloxacin, Nelfinavir, Nicardipine, Nilotinib, Norfloxacin, Nortriptyline, Ofloxacin, Olanzapine, Omeprazole, Ondansetron, Osimertinib, Oxaliplatin, Oxytocin, Paliperidone, Panobinostat, Papaverine HCl, Paroxetine, Pasireotide, Pazopanib, Pentamidine, Perphenazine, Pimozide, Pipamperone, Probucol, Procainamide, Promethazine, Propofol, Quetiapine, Quinidine, Quinine, Rilpivirine, Risperidone, Ritonavir, Roxithromycin, Saquinavir, Sertraline, Sevoflurane, Solifenacin, Sorafenib, Sotalol, Sulpiride, Sultopride, Sunitinib, Tacrolimus, Tamoxifen, Telaprevir, Tetrabenazine, Tiapride, Tizanidine, Tolterodine, Toremifene, Torsemide, Trazodone, Trimipramine, Vandetanib, Vardenafil, Vemurafenib, Venlafaxine, Voriconazole, Vorinostat, Zotepin

Note: Please refer the comprehensive list of drugs, which include approved drugs overseas, associated with QT prolongation and/or Torsades de Pointes (QT Drug Lists by Risk Groups) provided by the Arizona Center for Education and Research on Therapeutics.⁵

Disallowed from screening until the Week 12 Follow-up Visit

• Prescription drugs for improvement of hepatic function which could potentially affect to hepatic function including AST and ALT (eg. glycyrrhizinate, ursodeocycholic Acid)

Disallowed from screening onwards until the end-of-treatment

- Immunomodulators (eg, cyclosporine, interleukins, or systemic corticosteroids in immunosuppressive dose)
- Any herbal or nutritional products for HCV treatment including silibinin, silybin, and silymarin (milk thistle)
- Antiarrhythmics: mexiletine, systemic lidocaine, and propafenone
- Beta-blockers
- Proton-pump inhibitors (eg, rabeprazole)
- Ca-channel blockers (eg, amlodipine, bepridil, diltiazem, felodipine, nifedipine, nisoldipine, verapamil)
- Na-channel blockers (eg, lidocaine, mexiletine, moricizine, propafenone, tocainide)
- K-channel blockers (eg, bretylium, dronedarone, ibutilide, dofetilide)

Disallowed from 2 weeks before baseline and during the Treatment Period

- Potent and moderate CYP3A4 inducers, such as:
 - Antiepileptics: carbamazepine, oxcarbazepine, (fos)phenytoin, phenobarbital
 - Antituberculosis drugs: rifabutin, rifampicin, and rifapentine
 - Systemic dexamethasone (if more than a single dose)
 - Miscellaneous: products containing *Hypericum perforatum* (St. John's Wort)
- P-gp inhibitors

Disallowed from baseline onwards until the end-of-treatment

- Potent and moderate CYP3A4 inhibitors, such as:
 - Antibiotics (systemic): troleandomycin, and telithromycin
 - Antiretrovirals: (fos)amprenavir, delavirdine, darunavir, etravirine, indinavir, lopinavir, nevirapine, tipranavir
 - Miscellaneous: cobicistat-containing products
- CYP3A substrates with narrow therapeutic index, eg:
 - Antihistamines astemizole and terfenadine.
 - Gastrointestinal/gastroesophageal reflux disease drugs: cisapride.

Disallowed from 14 days before baseline until the Week 4 Follow-up Visit

Oral contraceptives

Key: CYP=cytochrome P450; HCV=hepatitis C virus; P-gp=P-glycoprotein Notes:

- The list of disallowed concomitant medication is not exhaustive; for drugs falling in one of the categories defined by respective CYP or P-gp interaction and not mentioned by name, the sponsor should be contacted to determine whether the drug can be allowed.
- As sacubitril can interfere with BNP measurement, sacubitril-containing products are disallowed from screening until Week 4 Follow-up Visit.

An overview of concomitant medication that should be used with caution is presented in Table 2.

Table 2: Concomitant Medication to be Used With Caution

The following concomitant medication is allowed, but should be used with caution and be started at the lowest possible dose, with monitoring of adverse events and desired efficacy.

- Analgesics: ergoloid mesylates, ergotamine tartrate, dihydroergotamine, and methylergonovine
- Lipid-lowering drugs: atorvastatin, lovastatin, pitavastatin, pravastatin, rosuvastatin, and simvastatin.
- Phosphodiesterase-5 inhibitors: sildenafil and tadalafil
- Sedatives/anxiolytics: midazolam and triazolam
- Acid-reducing agents: antacids (eg, aluminium and magnesium hydroxide) (recommended to separate antacid and study drug administration by 4 hours), H₂-receptor antagonists (eg, ranitidine) (may be administered simultaneously with or 12 hours apart from study drugs).

The manufacturer's prescribing information for SMV and the IBs of AL-335 and ODV may be consulted for additional details on drug-interaction potential.

The sponsor must be notified in advance (or as soon as possible thereafter) of any instances in which prohibited therapies are administered. For any concomitant therapy given as a treatment for a new condition or a worsening of an existing condition, the condition must be documented in the Adverse Event Section of the eCRF.

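### Table 2 of Section 8 allows H2-receptor antagonists as a class, although Table 1 bars famotidine, a member of that class, by name as a QT-listed drug

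*Protocol*

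**What the plan says.** Table 1 of Section 8 (Disallowed Medications) groups drugs by the period for which they are barred. Under the heading "Disallowed from screening until the end of the study" it gives a general rule, "All concomitant medications with a potential to prolong QT interval (eg, digoxin"), followed by a printed list of drugs associated with QT prolongation or Torsades de Pointes. That list includes the run "Escitalopram, Esomeprazole, Famotidine, Fingolimod, Flecainide" and, near its end, "Vandetanib, Vardenafil, Vemurafenib".

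Table 2 (Concomitant Medication to be Used With Caution) states that its contents are allowed, "but should be used with caution and be started at the lowest possible dose". It has five entries: analgesics, lipid-lowering drugs, phosphodiesterase-5 inhibitors, sedatives/anxiolytics and acid-reducing agents. The last covers antacids and H2-"receptor antagonists (eg, ranitidine) (may be administered simultaneously with or 12 hours apart from study drugs").

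Three provisions give the disallowed list its force. Section 4.2, criterion 7, excludes anyone taking a therapy disallowed in Section 8. The text of Section 8 excludes patients on Table 1 medication. Section 10.2 requires study treatment to be discontinued if a subject needs a listed drug. None of the three mentions Table 2.

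**The concern.** Read as written, Table 2 permits a drug that Table 1 prohibits. A prescriber has some reason to rely on the Table 2 entry. Table 1 bars proton-pump inhibitors as a class until end of treatment, so a subject who needs acid suppression on treatment is left with antacids or an H2-receptor antagonist. Table 2 then supplies self-contained dosing advice for the latter. A site could choose famotidine in good faith without searching a long alphabetical list under a QT heading.

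That would be a prohibited-medication deviation and, under Section 10.2, would put the subject's study treatment in question. It would also place a QT-listed co-medication in a study whose primary endpoint is safety, ECGs included, with about 20 subjects per cohort. Sections 1.3.2.2 and 1.3.3 name the ban on QT-prolonging co-medication as one of the protections against the cardiac risk of odalasvir. Section 9.2.8.7 requires odalasvir to be stopped for a confirmed QTc above 500 msec and requires evaluation with the sponsor for a rise above 60 msec. Either finding would be harder to attribute in a subject also taking famotidine.

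**Working it through.** The protocol states no figure on this point, so the check is a comparison of the two tables, with a count to see how far the overlap extends.

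**Step 1: set the entries side by side.**

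| | Table 1 | Table 2 |
|---|---|---|
| Famotidine | Named in the QT list; barred from screening to end of study | Not named, but falls within the H2-receptor antagonist class, which is allowed |
| Ranitidine | Not in the printed QT list | Given as the example of the allowed class |
| Vardenafil | Named in the QT list; barred for the same period | Not reached: the entry reads "inhibitors: sildenafil and tadalafil" |

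That famotidine is an H2-receptor antagonist and vardenafil a phosphodiesterase-5 inhibitor is general pharmacology. The protocol does not state either.

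**Step 2: measure the overlap.** Four of the five Table 2 entries are closed lists of named drugs:

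- analgesics: 4
- lipid-lowering drugs: 6
- phosphodiesterase-5 inhibitors: 2
- sedatives/anxiolytics: 2
- total: 4 + 6 + 2 + 2 = 14

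The QT list printed in Table 1 has 135 distinct names. Matched by name, 0 of the 14 appear among the 135, and ranitidine does not appear either. The closed lists therefore do not collide with Table 1. The phosphodiesterase-5 entry avoids the barred member of its class by naming only two others. The H2 entry is an open class without an exception, and through famotidine it reaches into the QT list.

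**Step 3: look for a rule that reconciles the tables.** No sentence in Section 8 makes Table 2 subject to Table 1. The note under Table 1 that sends sites to the sponsor is limited to "drugs falling in one of the categories defined by respective CYP or P-gp interaction and not mentioned by name, the sponsor should be contacted". Famotidine is named, and it is listed for QT rather than for a CYP or P-gp interaction, so the note does not apply to it. The exclusion and discontinuation provisions bind on the disallowed list without qualification, which supports reading Table 1 as controlling, but they leave the Table 2 permission uncorrected.

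**The case against.** The strongest reply is that the protocol already decides the matter. A named, unconditional ban prevails over a general class allowance, the ban sits within a blanket rule against QT-prolonging drugs, and nothing presents Table 2 as an exception to Table 1. Section 8 has to be read cumulatively in other places too. Proton-pump inhibitors are barred as a class until end of treatment, while omeprazole, esomeprazole and lansoprazole are barred by name until the end of the study, and the stricter entry must be followed. On this view the H2 entry is caution and timing advice for drugs not otherwise barred, and what is missing is a cross-reference.

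Other safeguards limit the harm. Section 4 requires the sponsor to be consulted on eligibility questions and allows no waivers. Section 8 requires all concomitant therapy to be recorded and the sponsor to be notified, in advance or as soon as possible afterwards, when prohibited therapy is given. Triplicate ECGs are taken at every scheduled on-treatment visit.

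Most of this stands: Table 1 should be taken to control, and the safeguards reduce the consequences. It does not make the Table 2 entry correct. The proton-pump inhibitor example concerns two prohibitions of different length, and a site can satisfy both by following the longer one. Here one table allows what the other forbids. Notification also helps only if the site recognises that the drug is prohibited, which is what Table 2 obscures.

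**Conclusion.** The concern holds and is minor. Table 2, as written, permits famotidine while Table 1 prohibits it, and no precedence sentence resolves the conflict. Its textual extent is the single H2 entry. The likelihood and size of any effect on the data cannot be stated, because the protocol gives neither a rate of H2-antagonist use nor a QTc effect for famotidine. No endpoint definition, analysis or sample-size statement changes.

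The conclusion rests on one fact from outside the document, the drug class of famotidine. The practical risk further assumes that a site acts on Table 2 without checking Table 1.

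**What to change.** Reword the Table 2 entry to: H2-receptor antagonists (eg, ranitidine), except famotidine and any other agent on the Table 1 QT list. Add one sentence to Section 8 stating that Table 1 governs wherever a Table 2 class entry overlaps a drug disallowed in Table 1. The exception alone would settle famotidine; the sentence also covers any similar overlap.

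The cost is one line and one sentence, plus a notice to sites. Section 17.1 requires a formal amendment with IEC/IRB approval, so the change is best bundled with another amendment rather than issued on its own.

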9. STUDY EVALUATIONS

9.1. Study Procedures

9.1.1. Overview

The TIME AND EVENTS SCHEDULE summarizes the frequency and timing of all measurements and evaluations applicable to this study.

Additional serum or urine pregnancy tests may be performed, as determined necessary by the investigator or required by local regulation, to establish the absence of pregnancy at any time during the subject's participation in the study.

Repeat or unscheduled samples may be taken for safety reasons or for technical issues with the samples.

Dosing of cohort 2 with patients with compensated cirrhosis will only start after a DRC has reviewed all available relevant safety data when the first 6 subjects in cohort 1 completed the Week 4 visit (including but not limited to AE, Serious AE [SAE], clinical laboratory test) and no

NCT02993250

Clinical Protocol 64294178HPC2003 Amendment 5

new or unexpected events, which are considered clinically significant, are detected. Based on this review, start of dosing in cohort 2 will be notified to investigators and be opened via an interactive web response system (IWRS) by the sponsor. Enrollment in cohort 1 will be kept ongoing during the data review process.

For subjects enrolled in cohort 1, approximately 330 or 370 mL of blood will be drawn during the study, and for subjects enrolled in cohort 2, approximately 390 or 430 mL of blood will be drawn during the study, depending on the participation in the rich PK substudy.

The first screening assessment has to be performed within 6 weeks prior to the Baseline Visit (ie, Day 1). The timing of visits during the Treatment Period should be based on the start date of study drug intake (ie, at the Baseline Visit on Day 1). The subject should be encouraged to come within the following time windows:

- For visits on Days 2 and 3: no time window allowed.
- For visit at Week 1 of the Treatment Period: -1 to +1 day.
- For visits at Weeks 2, 3, 4, and 6, of the Treatment Period: -2 to +2 days.
- For visits at Weeks 8 and 10, of the Treatment Period: -2 to +2 days (Cohort 2 only).
- For the EOT Visit: -1 to +1 day.
- For visit at Week 4 of follow-up: -3 to +3 days.

For all other scheduled visits during the 24-week Follow-up Period: -7 to +7 days. These time windows may be shortened when approaching a data analysis. If this is the case, sites will be informed.

9.1.2. Screening Period

Within 6 weeks prior to the Baseline Visit and after signing and dating the ICF, the first screening assessment should be performed. Screening assessments as indicated in the TIME AND EVENTS SCHEDULE may be split over more than one visit. After informed consent has been obtained, each subject should be registered via an IWRS (See the IWRS manual).

A complete physical examination (including height, body weight, and body systems and, if considered necessary by the investigator based on the subject's past and present medical history, breast, genitals, or rectal examination) will be conducted and the following will be recorded for each subject: demographics, medical and surgical history, concomitant diseases, prestudy therapies, and vital signs.

Echocardiography and triplicate ECG will be performed at screening. Electrocardiogram and echocardiography findings will be recorded for each subject.

Blood sampling for determination of the HCV geno-/subtype and HCV RNA level will be performed. In addition, a blood sample for hematology and biochemistry, and a urine sample for

urinalysis (including a urine drug screening test) will be collected. Hepatitis A, B, and C serologic testing, and HIV-1 and HIV-2 serologic testing will also be performed.

A serum pregnancy test will be performed in women of childbearing potential. The FSH level will be tested in female subjects who are postmenopausal for less than 2 years.

Presence or absence of cirrhosis will be determined by a fibroscan. Subjects without cirrhosis are defined as having had a fibroscan with a documented result of ≤ 12.5 kPA (performed within 6 months of baseline/Day 1) or liver biopsy within 6 months of baseline/Day 1 showing absence of cirrhosis (METAVIR score of F0-F3 or Ishak score <5). Subjects with compensated cirrhosis are defined as having a fibroscan (performed prior report or during Screening Period) with a documented result of >12.5 kPA or liver biopsy (prior report or during Screening Period) showing cirrhosis (eg, METAVIR score of F4 or Ishak score ≥ 5).

For subjects with cirrhosis, an ultrasound scan, CT scan, or MRI should be performed within 3 months prior to baseline/Day 1, with no findings suggestive of hepatocellular carcinoma.

Occurrence of clinical events related to AEs, pregnancies, and use of concomitant therapies will be reported from the time a signed ICF is obtained.

The investigator will assess the overall eligibility of the subject to participate in the study once all screening values and results of any other required evaluations are available and document this in the source documents. Retesting of laboratory values (eg, safety laboratory or HCV RNA) that lead to exclusion will be allowed once using an unscheduled visit during the Screening Period to assess eligibility. In exceptional cases, the Screening Period can be extended, if discussed with and approved (documented) by the sponsor, eg, if not all the test results become available during the allocated 6 weeks; this will be evaluated on a case-by-case basis.

9.1.3. Open-label Treatment Period

If eligible, subjects to be treated in the study will come for the Baseline Visit (Day 1). Investigators should ensure that all study enrollment criteria have been met during screening. If, after screening but prior to the first dose of study drug, a subject's clinical status (including any available laboratory results or receipt of additional medical records) changes, such that he or she no longer meets all eligibility criteria, then the subject should be excluded from participation in the study. After the investigator confirms that a subject met all criteria, site staff should register the subject via an IWRS on Day 1. At the Week 4 and EOT or early withdrawal visit, site staff should enter the information via an IWRS (See the IWRS manual).

Information on drug dosage and administration is provided in Section 6, and information on the use of the medication diary is provided in Section 7.

All baseline assessments need to be performed before study drug intake in the morning. The timing of the baseline morning dosing should be recorded in the eCRF.

A pharmacogenomic blood sample for host *IL28B* genotyping will be collected at baseline.

Targeted physical examinations (ie, physical examinations directed at specific body systems as required based on the medical history and overall clinical presentation) (including body weight), vital sign measurements, and blood and urine samples for clinical laboratory assessments will be performed at the time points indicated in the TIME AND EVENTS SCHEDULE.

For female subjects of childbearing potential, a urine pregnancy test will be performed on-site on Day 1 and every 4 or 6 weeks as indicated in the TIME AND EVENTS SCHEDULE.

Blood sampling for the determination of the HCV RNA level (on Day 1, predose in the morning) and for viral sequencing will be performed at all scheduled visits. The HCV NS3/4A, NS5A, and NS5B regions will be sequenced pretreatment (at baseline) by default in all subjects and postbaseline in subjects not achieving SVR. Sequencing of additional samples may be triggered by the sponsor's virologist.

Hepatitis B virus DNA will be measured with PCR testing at the EOT Visit, or Treatment Withdrawal Visit, and may be evaluated at any time when there is a significant increase in the ALT or AST levels This only refers to subjects with antiHBc and/or antiHBs positive status at screening and not to subjects who have received HBV vaccine and are only antiHBs positive.

Occurrence of clinical events related to all AEs, whether serious or nonserious, pregnancies, and use of concomitant medication will be reported throughout the Treatment Period.

Echocardiography and triplicate ECG (at study approved facility) will be performed at the time points indicated in the TIME AND EVENTS SCHEDULE. Additional ECG or echocardiography may be done at any time during the study if clinically indicated in the opinion of the investigator.

All subjects will undergo sparse PK blood sampling (predose, between 2- to 4-hours postdose, and between 4- to 6-hours postdose) at the time points indicated in the TIME AND EVENTS SCHEDULE for the measurement of plasma concentrations of AL-335 (and metabolites), ODV, and SMV. At the EOT visit, intake of study drugs should take place on site when predose PK sampling (sparse and rich sampling) is performed. At Week 4, no sparse PK sample will be taken for subjects participating in the rich serial PK substudy.

In addition, rich serial PK sampling for AL-335 (and metabolites), ODV, and SMV will be performed in approximately more than 12 subjects (Cohorts 1 and 2 combined). Subjects participating in the rich serial PK substudy will undergo rich serial PK sampling at their Week-4 Visit, at 10 different time points within the dosing interval (see the TIME AND EVENTS SCHEDULE: Rich serial PK Assessments). All PK blood samples will be stored and analyzed at the discretion of the sponsor.

If study drug is discontinued prematurely, for reasons other than withdrawal of consent, a Treatment Withdrawal Visit should be scheduled as soon as possible after the EOT. The subjects will be followed up for 24 weeks after EOT, with visits as indicated in the TIME AND EVENTS SCHEDULE. If a subject discontinues treatment due to withdrawal of

consent, the subject will be offered an optional Treatment Withdrawal Visit, to be scheduled as soon as possible after withdrawal and/or a safety Follow-up Visit, which needs to be scheduled 4 weeks after EOT. At the safety Follow-up Visit, safety assessments of the Week 4 Follow-up Visit need to be performed.

A DRC will be established to monitor data with focus on the safety and on the general conduct of the study. Emerging safety data from this study will be reviewed at predetermined intervals.

